The second visit is Study Visit 1, which could be combined with the Screening Visit. At this visit retrospective data (from medical chart review) and current data will be collected. For patients who are able to attend the visit at the clinic data on a physical assessment, Expanded Disability Status Scale (EDSS), Patient-Reported Outcomes (PROs), cognitive assessments, AEs and concomitant medications will be collected. For all patients the following retrospective data will be collected: EDSS, Secondary Progressive MS (SPMS) conversion, details of subsequent DMDs, including physician questions on treatment decisions, date of first use of an ambulatory device or wheelchair, date of first time bedridden and relapse history from end of parent study to Study Visit 1. In ORACLE MS patients, CDMS conversion and PPMS diagnosis will be assessed as well. An optional blood sample for pharmacogenetic testing will be taken from patients who consent to the optional sampling at the clinic and who are seen at a site with available capabilities to store and ship these samples. Patients will also have the opportunity to provide pharmacogenetic samples after Study Visit 1 and up to 6 months from Screening (unless last patient enrolment has occurred, in which case the sample can only be collected at Study Visit 1).

For patients from whom in-person EDSS at clinic visit was not planned to be collected, a telephone EDSS questionnaire will be administered. Attempts should be made to administer the telephone EDSS within 14 days after informed consent was received for patients not attending the clinic visit.

Study data will be supplemented with information from the past clinical trial(s), which will be integrated for milestones such as interim analyses and, if needed, on a regular basis. It is the Sponsor, not the site, that is responsible for obtaining the information from the past clinical trial(s) study databases. However, the sites will be requested to provide some patient identifiers (e.g. patient number, parent study patient participated in, year of birth and gender) to match data being collected with previous data sets.

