The third potential clinic visit is Study Visit 2, which involves an MRI scan without gadolinium in approximately 150 patients who are willing to participate in this MRI sub-study. The sites that participate in the MRI sub-study will be selected primarily based on their technical capabilities to perform the required MRI assessments and the availability of the original MRI machine from the parent studies. The patients at these sites will be selected based on being able to fulfill the eligibility criteria (see Section 6.5.4.2), including the availability/consent of the patient to perform a new MRI and the provision of a urine pregnancy test within a week prior to the MRI assessment (for female patients of childbearing age). A serum pregnancy test is also acceptable if available as per standard of care (SOC). Verbal reporting of pregnancy status by the female patient is not acceptable. AEs and concomitant medications will also be reviewed and recorded during this visit. For patients who are not experiencing relapse at the time of screening, the duration between Screening Visit to Study Visit 1 is no more than 2 weeks, including for patients who are participating remotely and who are completing a telephone EDSS assessment only. For patients experiencing relapse, the duration between Screening and Study Visit 1 is between 4 weeks and 3 months. For patients selected to participate in the MRI sub-study, an additional visit will be required that will occur within a maximum of 3 months of Study Visit 1 (maximum 4 weeks from Study Visit 1 if last patient recruitment has occurred), and these patients' total study duration will likely be no more than 3.5 months if the patient was not experiencing relapse at Screening, or up to 6 months maximum in the case of relapse. For patients providing samples for pharmacogenetic testing, the time window for sample collection is up to a maximum of 6 months from Screening (unless last patient enrolled has occurred, in which case the testing must occur at Study Visit 1). Sites will be asked to enter any retrospective data into the electronic case report form (eCRF) for this study within 12 weeks of enrolling the patient. Participants who are eligible will be given the option of completing the screening, Study Visit 1, and 2 (where facilities for MRI are available) on the same day if prefer to do so and meet the eligibility criteria on that day (e.g. abstention from alcohol or cannabinoid products in the preceding 24 hours). Participants who are undergoing relapse or suspected relapse at the time of screening will be invited for Study Visit 1 after a stabilization period determined through consultation with the medical monitor.

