The in-person EDSS will be completed by the evaluating physician for those study participants who can come to the clinic for Study Visit 1. Alternatively, a telephone EDSS score can be determined by telephone interview in which trained clinical site staff member to administer the EDSS telephone questionnaire (Lechner-Scott, 2003). The telephone EDSS will be collected only from patients not attending clinic visits, and will be collected within 14 days of obtaining informed consent. Only one mode of the collection (in-person during a clinic visit, or by telephone) is required per patient. Retrospective EDSS scores will be ascertained from medical records for the time period between end of parent study to Study Visit 1 (when available).

Reasons for inability to come to the clinic for Study Visit 1 may include travel/migration, or limited mobility (bedridden), or clinical site restrictions due to COVID-19. In addition, patients may not want to come to the clinic for Study Visit 1 due to a lack of interest..

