8.1.2 Other Assessments

8.1.2.1 Patient-reported Outcomes/Quality of Life: EQ-5D-3L

The 3-level version of the EuroQoL-5 Dimension questionnaire (EQ-5D-3L) will be administered at Study Visit 1. The EQ-5D-3L is a validated, self-administered, generic, utility instrument that includes 5 single-item dimensions: mobility, self-care, usual activities,

³ Unlike the 2010 McDonald criteria, no distinction between symptomatic and asymptomatic MRI lesions is required.

pain/discomfort, and anxiety/depression (EuroQoL Group, 1990). Study participants must choose between 3 levels of difficulty in accomplishing tasks in each dimension. The questionnaire also contains a Visual Analog Scale for the study participants to rate their current health state from 0 (worst imaginable health state) to 100 (best imaginable health state).

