- All participant study data will be recorded on electronic case report form (eCRFs) or transmitted to the Sponsor or designee electronically (e.g., laboratory data). The Investigator is responsible for verifying that data entries are complete, accurate, legible, and timely by physically or electronically signing the case report form (CRF). Details for managing CRFs are in the Study Reference Manual.
- For PRO data (e.g., QoL and cognitive assessments), paper PRO will be used.
- The Investigator must maintain accurate documentation (source data) that supports the information in the CRF.
- The Investigator must permit study-related monitoring, quality assurance audits, IRB/IEC review, and regulatory agency inspections and provide direct access to the study file and source data.

-
- Monitoring details describing strategy (e.g., risk-based initiatives in operations and quality such as Risk Management and Mitigation Strategies and Analytical Risk-Based Monitoring), methods, responsibilities and requirements, including handling of noncompliance issues and monitoring techniques (central, remote, or on-site monitoring) are in the Monitoring Plan.
 - The Sponsor or designee is responsible for data management of this study, including quality checking of the data and maintaining a validated database. Database lock will occur once quality control and quality assurance procedures have been completed.
 - Study monitors will perform ongoing source data verification to confirm that data in the CRF are accurate, complete, and verifiable; that the safety and rights of participants are being protected; and that the study is being conducted per the currently approved protocol and any other study agreements, ICH GCP, and all applicable regulatory requirements.
 - Records and documents, including signed ICFs, pertaining to the conduct of this study must be retained by the Investigator for 15 years after study completion, unless local regulations, institutional policies, or the Sponsor requires a longer retention. No records may be destroyed during the retention period without the Sponsor's written approval. No records may be transferred to another location or party without the Sponsor's written notification.

Source Documents

- Source documents provide evidence for the existence of the participant and substantiate the integrity of the data collected.

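### The EQ-5D-3L is planned for clinic attenders only; remote participants, who may be remote because they are bedridden, are left out, so quality of life is likely biased upward by an unknown amount

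*Protocol*

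**What the plan says.** **Who is asked.** Protocol Section 4.1 introduces the prospective Visit 1 data for patients "who are able to attend the visit at the clinic data on a physical assessment, Expanded Disability Status Scale (EDSS), Patient-Reported Outcomes (PROs", and goes on to cognition, adverse events and concomitant medication. A second list, for all patients, follows directly. It holds retrospective chart items only, and patient-reported outcomes are not among them. Later in the same section, the sentence on visit windows covers patients without relapse, "including for patients who are participating remotely and who are completing a telephone EDSS assessment only".

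**Who is remote.** Section 8.1.1.1 says the reasons for not attending "may include travel/migration, or limited mobility (bedridden), or clinical site restrictions due to COVID-19". It adds that "patients may not want to come to the clinic for Study Visit 1 due to a lack of interest".

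**How the instrument is given.** Table 1 in Section 1.3 gives the EDSS a telephone alternative and gives the EQ-5D-3L none. Section 8.1.2.1 states: "The EQ-5D-3L is a validated, self-administered, generic, utility instrument that includes 5 single-item dimensions". Appendix 2 adds: "For PRO data (e.g., QoL and cognitive assessments), paper PRO will be used".

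**How it is analysed.** SAP 14.3.3 summarises Visit 1 values and change descriptively. Its only missing-data rule concerns an absent pre-treatment score. SAP 9.5 gives imputation rules for dates and none for the EQ-5D-3L. Protocol 9.4.1 leaves multiple imputation as an option. The objective in Section 3 refers to study participants, not attenders, and the EQ-5D-3L is part of the interim analysis (Protocol 9.4.2, SAP 6.4).

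**The concern.** The EQ-5D-3L asks about mobility, self-care and usual activities. A patient who stays at home because of disability is missing from the measure that disability affects most, so for that part of the remote group the missingness depends on the outcome.

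The plan protects its other long-term endpoints from this loss. The EDSS has a telephone version, and mobility milestones come from charts for everyone. The EQ-5D-3L has no such route, and no reason is given.

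No later step repairs the gap. The selection-bias comparison in SAP 11.1 sets participants against non-participants, so it cannot detect a loss among participants. Under Protocol 7.2 a patient may remain in the study without completing patient-reported outcomes. What is at stake is how far the reported quality of life describes the whole followed-up group.

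**Working it through.** The plan states no sample size, standard deviation or expected value for the EQ-5D-3L, so there is no figure to reproduce. The check is of direction and possible size, using the EQ VAS (0–100, Section 8.1.2.1).

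**Inputs, all assumed because the documents give none of them**

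- r, share of living participants who are remote: 5–30%.
- b, share of remote participants who are bedridden: 10–50%.
- D, VAS deficit of bedridden remote patients against attenders: 20–40 points.
- A, VAS advantage of the other remote patients over attenders: 0 at first.

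**Formula.** With attender mean C, the mean over all living participants is

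(1−r)C + r[b(C−D) + (1−b)(C+A)] = C − r[bD − (1−b)A].

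The attender-only mean is therefore too high by r[bD − (1−b)A].

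**Results with A = 0 (bias = r × b × D)**

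| r | b | D | Bias, VAS points | r × b |
|---|---|---|---|---|
| 5% | 10% | 20 | 0.1 | 0.5% |
| 20% | 25% | 20 | 1.0 | 5% |
| 20% | 25% | 40 | 2.0 | 5% |
| 30% | 50% | 40 | 6.0 | 15% |

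The last column is the share of all participants who would be both bedridden and remote. Protocol 9.2 uses 5%, 10% and 15% as possible wheelchair proportions. If that range is taken for the whole primary endpoint, the 6-point corner needs everyone at its upper value to be bedridden and at home. The middle settings already need as many such patients as its lower value.

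**Could the other remote patients cancel it?** The bias is zero when A = bD/(1−b).

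- At b = 10%: A = 2.2 (D = 20) to 4.4 (D = 40).
- At b = 25%: A = 6.7 to 13.3.

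**Under-representation.** Suppose 10% of participants meet the wheelchair/bedridden endpoint, half of those are remote, and 5% of the rest are remote. Their share of the EQ-5D-3L sample is 0.10 × 0.5 / (0.10 × 0.5 + 0.90 × 0.95) = 0.05/0.905 = 5.5%, against a true 10%. At 5% and 15% prevalence the shares are 2.7% and 8.5%.

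**Mobility item (levels 1–3).** Assume attenders average 1.6, r = 20%, and 25% of remote patients score 3 with the rest at 1.6. The all-participant mean is 1.6 + 0.20 × 0.25 × 1.4 = 1.67, a gap of 0.07.

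**Change scores.** The same bias carries over to the mean change so far as bedridden remote patients did not already score differently at the parent-study reference visit.

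**The case against.** **The text is less than explicit.** The phrase about a telephone EDSS alone sits in a sentence on visit windows and may only contrast telephone with in-person EDSS. Table 1 and Section 8.1.2.1 place the EQ-5D-3L at Study Visit 1 without restricting it to the clinic, and Figure 2, on remote visits, is not reproduced in the text available. This stands in part: the exclusion rests mainly on the two lists in Section 4.1. Those lists are clear enough, though, and no remote route is described anywhere.

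**Most reasons for being remote are not about disability.** Travel or migration, COVID-19 restrictions and lack of interest have no stated link to health. This stands. A reader might infer that the whole remote group is badly off. Giving all of them a 10–25 point deficit at 10–30% remote would yield 1.0–7.5 points, and putting all of a 20% remote group at mobility level 3 would give 0.8 × 1.6 + 0.2 × 3 = 1.88. The documents do not support that premise.

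**Severe disability is thinned, not absent.** A reader might infer that the result covers only patients well enough to travel. Wheelchair users are not barred from attending, and SAP 14.1 takes EDSS of 7 or more at Study Visit 1 as a source for the primary endpoint.

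**Some handling exists.** Missing counts are reported (SAP 9.5), Visit 1 EDSS is listed by phone and site (SAP 11.1), and Protocol 9.4.1 allows imputation under missing-not-at-random assumptions. These steps help, but they are generic or optional, and SAP 14.3.3 applies none of them to the EQ-5D-3L.

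**The endpoint is tertiary and exploratory.** True, and it limits the weight of the point. The EQ-5D-3L was nevertheless chosen for the interim results.

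**Conclusion.** The collection gap is in the text and does not depend on any assumption: as written, the quality-of-life objective is answered from clinic attenders. Because being bedridden is a named reason for non-attendance, the likely direction is toward better health.

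The size is not known. Under the assumed ranges, with the other remote patients equal to attenders, it is about 0.1–6 VAS points, with 1–2 at 20% remote and 25% of those bedridden. The upper end is hard to reach within the protocol's own planning proportions. The direction could reverse if the other remote patients were sufficiently healthier than attenders; nothing in the documents suggests this, and nothing excludes it.

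Two stronger conclusions might be drawn and are not supported. One is that quality of life is demonstrably overstated: that is an expectation, not a result. The other is that the exposed versus never-exposed comparison is biased: that would require the make-up of the remote group to differ between them, on which the documents are silent.

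This is an inexpensive improvement worth making to a tertiary endpoint. It does not touch the primary result.

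**What to change.** **Protocol Sections 1.3, 4.1 and 8.1.2.1.** Have remote participants complete the EQ-5D-3L after consent, either by telephone during the EDSS call already planned within 14 days or on a paper form sent once consent has been received. The form should not go out with the consent papers, since Section 8.1 requires consent before study-specific assessments. Record the mode of administration.

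**SAP 14.3.3.** Report EQ-5D-3L completion, Visit 1 values and change, overall and by clinic or remote mode.

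**Where remote EQ-5D-3L cannot be obtained**, including for patients already past their visit:

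- report completion by mode and by EDSS category;
- limit the conclusion to clinic attenders;
- add a missing-not-at-random sensitivity analysis, for example by predicting the missing scores from the available telephone or chart EDSS and then lowering them over a stated range. Few attenders may have very high EDSS, so this step extrapolates and should be labelled as such.

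**Cost.** A protocol amendment needing ethics approval, in a study of about 108 sites in 30 countries, plus one eCRF field and a short addition to a call already made. The SAP changes alone need no new data collection, since Visit 1 EDSS is already listed by phone and site. The downside is a mode-of-administration difference in remote patients, which reporting by mode shows but does not remove. Interim results already disseminated cannot be repaired, only qualified.

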4.2 Scientific Rationale for Study Design

The purpose of this study is to explore the long-term outcomes, durability of effect, and real-world treatment patterns in patients previously participating in the parent studies. This exploratory Phase IV study includes retrospective and prospective assessments. It will involve the collection of long-term retrospective data through abstraction of medical charts/records. For patients participating in the prospective assessment of the study, additional data will be collected at Study Visit 1 and patients will be asked for an optional blood sample. For a subset of patients, an MRI assessment will be performed at Study Visit 2, which will occur within a maximum of 3 months after completing Study Visit 1 (maximum 4 weeks from Visit 1 if last patient recruitment has occurred). No IMP will be administered as part of this study.

The primary objective of this study is to evaluate long-term mobility after treatment with Cladribine Tablets or placebo in the parent studies. This will be evaluated by the primary endpoint, the proportion of study participants using a wheelchair (defined as unable to walk beyond approximately 5 meters even with aid, essentially restricted to wheelchair; wheels self in standard wheelchair and transfers alone; up and about in wheelchair some 12 hours a day) the majority of the time in the 3 months prior to Study Visit 1 or participants are bedridden any time prior to Study Visit 1, determined via EDSS score of 7.0 or higher, or alternative clinical description data in medical records. This primary endpoint was selected as a reliable and valid measure of long-term mobility following treatment with IMP in the parent studies. This endpoint was agreed upon by the Steering Committee members as one that is practical for this ambispective study design, as use of a wheelchair or being bedridden is a disability milestone for patients with MS and will likely be recorded in medical charts, either as a clinical description or via an EDSS score of 7.0 or higher. This endpoint is also practical to evaluate at Study Visit 1, thus maximizing the amount of data that can be collected for the primary endpoint in this study.

The secondary objective is the comparison of clinical characteristics between long-term responders (defined as study participants who did not demonstrate any evidence of disease reactivation based on Investigator assessment of clinical and imaging outcomes until Year 4 or later following their last dose of IMP and who did not receive disease modifying treatment until Year 4 or later following their last dose of IMP) compared to those who started on alternate therapy less than 4 years following their last dose of IMP for the combined parent study populations. This secondary objective helps to fill an important data gap, which is understanding treatment sequencing following Cladribine Tablets and specifically understanding if there are differences in clinical characteristics (gender, age/year of birth, race, ethnicity, education, employment status, disease duration [years], current disease modifying treatment, time since last relapse [months], and disease classification [RRMS or SPMS]) between study participants who did and did not start on an alternative therapy within 4 years of their last dose of IMP in the parent studies.

The study will enroll study participants with MS who participated in the CLARITY/CLARITY-EXT clinical trials and who received ≥ 1 course of IMP (Cladribine Tablets or placebo), or with their FCDE who were randomized in the ORACLE MS study and received ≥ 1 course of IMP (Cladribine Tablets or placebo). Data collection for this study is based on study participants recruited into previously conducted clinical trials which had

defined inclusion and exclusion criteria. Therefore, the chosen inclusion criteria (Section 5.1) aim to be as inclusive as possible to maximize the number of study participants from the parent studies who can be enrolled, while allowing for the patient or their proxy/caregiver/legal representative (in cases where an ICF waiver will not apply) to consent to allow the collection of retrospective data and/or prospective data in order to maximize the data that can be collected in this exploratory study. The chosen exclusion criteria (Section 5.2) will protect the safety of study participants by excluding particularly vulnerable individuals.

4.3 Justification for Dose

Not Applicable.

4.4 End of Study Definition

A participant has completed the study if he/she has completed all study parts, including the last visit and/or the last scheduled procedure shown in Section 1.3 (Schedule of Activities).

The end of the study is defined as the date of the last patient's last visit. For study participants taking part in the main study only (i.e. for participants not participating in the MRI sub-study), a participant has completed the study if he/she has completed all study parts, including the Study Visit 1, which will be the last patient's last visit collected for the study. For those also taking part in the MRI sub-study, the Study Visit 2 will be the last study participant's last visit.

A clinical study protocol may not be considered closed as long as:

- Visits specified by the protocol are still taking place, or
- Procedures according to the protocol are still being undertaken in any patient.

During study participation and once patients have concluded their participation in this study, they will continue to be treated as part of their usual practice and care.

5 Study Population

The study population will be patients with MS randomized in the CLARITY or CLARITY-EXT study who have received ≥ 1 course of IMP (Cladribine Tablets or placebo) or patients with their FCDE randomized in the ORACLE MS study who have received ≥ 1 course of IMP.

The criteria in Sections 5.1 (Inclusion Criteria) and 5.2 (Exclusion Criteria) are designed to enroll only participants who are appropriate for the study; thereby, ensuring the study fulfills its objectives. All relevant medical and nonmedical conditions should be taken into consideration when deciding whether a participant is suitable for this study.

Prospective approval of protocol deviations to inclusion and exclusion criteria, also known as protocol waivers or exemptions, is not permitted.

Before performing any study assessments that are not part of the participant's routine medical care, the Investigator will confirm that the participant or the participant's proxy/caregiver/legal representative has provided written informed consent, or an ICF waiver is in place, if permitted by local regulation and approved by the relevant EC/IRB.

